### ***Anthropometric and clinical measures (collected at baseline and 3 months unless otherwise noted)***

Weight: will be objectively measured at the participant’s home. We will instruct participants to weigh themselves in light clothing, without shoes, on the cellular-enabled scales at each assessment time point.

Height (baseline only): Participants will provide self-reported height using a single item from Behavioral Risk Factor Surveillance System and adapted for use in the NCI’s Health Information and National Trends Survey.

Body Mass Index (BMI). Height and weight will be used to calculate BMI (kg/m^2).

Fried Frail Index. Frailty will be assessed among all participants with a Frailty Index (all participants) previously used by Co-I [name] among AYA survivors. The FRAIL Questionnaire includes five components that reliably predict declining health function and mortality without requiring a face-to-face evaluation. The items assess: 1) self-reported fatigue (PROMIS Fatigue Short form), 2) weight loss, 3) comorbidities (11 items from UNC Health Registry Comorbidity Assessment), 4) difficulty with ambulation (1 item from PROMIS Physical Function Short Form), and 5) ability to overcome resistance (1 item from PROMIS Physical Function)). The number of positive responses for these components is summed to create the FRAIL index (range 0–5) and characterized as 0-1: robust, 2: prefrail, and 3+: frail. Changes in individual components and overall frailty scores will be assessed.

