## PROTOCOL SYNOPSIS

Study Title	A pilot randomized factorial trial to promote physical activity and healthy eating among young adult cancer survivors
Clinical Phase	NA
Study Rationale	Few studies have tested PA interventions specifically for YACS, and no studies have tested nutrition interventions among this population. To accelerate science in this area, we propose a pilot randomized factorial trial as part of the preparation phase of the Multiphase Optimization Strategy (MOST) framework to test the feasibility, acceptability, and effects of a digital PA and nutrition intervention designed specifically for YACS. Previous interventions have demonstrated the importance of self-regulation (i.e., self-monitoring of behaviors, small changes, goal setting and feedback) approaches to improve PA and nutrition behaviors among young adults and YACS. We aim to leverage our prior work to deliver a theory-based intervention using digital tools to simplify self-monitoring of PA, and dietary monitoring to provide tailored behavioral goals and messages to support increased physical activity and diet quality among YACS.
Study Objective(s)	
Primary
 

• To evaluate the feasibility of a theory-based, mobile PA and nutrition intervention, as characterized by the participation, accrual, and retention rates at 3-months.

 
Secondary
 

• To evaluate acceptability of the intervention as characterized by ratings of program acceptability and satisfaction at 3-months.

• To evaluate the adherence to the intervention as measured by daily self-monitoring of activity (Fitbit) and dietary tracking (Traffic Light Approach) from baseline to 3-months based on experimental conditions.

• To estimate the main effects of each of four intervention components on changes in behavioral measures (Fitbit measured MVPA and healthy eating index (HEI) using the NCI's 24-hour Recall (ASA-24)) at 3-months.

• To estimate the main effects of each of four intervention components on changes in secondary outcomes including anthropometric (weight), clinical (Fried physical phenotype using the FRAIL index) and psychosocial measures (health related quality of life) at 3 months.

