**Unsafe Rate of Weight Loss:** Participants will not receive an intervention designed to produce weight loss, however, making dietary changes and increasing PA can produce a gradual, modest rate of weight loss. The intervention focuses on making small daily changes to their eating in service of shaping dietary quality over

time. Thus, although unlikely, it is still possible that some participants could experience excessive weight loss at a rate that is unsafe. We will carefully monitor rate of weight loss over the course of the study, and take appropriate action as detailed below to ensure participant safety.

Risk of wearable devices. There is also the possibility of minor skin irritation associated with wearable activity tracker devices.

Risk to privacy and/or confidentiality. We expect a breach of confidentiality to be rare or infrequent. Most communication during the study period will take place via telephone, direct emails, text messages, or through the smartphone app—either to deliver questions, conduct assessments, or remind participants to complete questionnaires. We do not anticipate any risks of harm as a result of these communications; however, there is always a possibility that their scale data, tracker data, or activity in the app will be intercepted.

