### **b. Protections Against Risk**

Protections against Psychological Risks: As noted above, participants are not required to share this information and can elect not to share sensitive and confidential information with the study. Participants will be encouraged to contact the Principal Investigator if they feel they have incurred any emotional distress as a result of study participation. As this is a voluntary study, a participant is free to exit at any point if discomfort should occur.

Protections against Physical Risks: To ensure medical readiness to begin physical activity, participants will complete a physical activity readiness questionnaire (PAR-Q). The PAR-Q assesses for the following medical conditions: heart problems, chest pains, faintness or dizzy spells, high blood pressure, bone or joint problems such as arthritis that has been or could be aggravated by exercise, prescription medication use, and other medical reasons why exercise would not be advisable. Participants endorsing yes to any items 1-4 on the PAR-Q (experience of heart problems, frequent chest pains, faintness or dizziness, bone or joint problems) will be excluded from the study. We also will monitor any major musculoskeletal problems that develop during the intervention (e.g. broken bones) using a medical events questionnaire at 6 weeks and 3 months and will determine whether these appear related to our study. Participants who develop musculoskeletal problems or other health problems that may affect safe participation will be instructed to stop exercising until the problem resolves and their physician approves resumption of physical activity.

All participants will be advised about safe weight loss practices including dietary change and increasing physical activity at their initial study visit. Participants will be advised to gradually increase their physical activity and to

use walking as a primary form of activity and will be taught that the appropriate rate of weight loss is 1 to 2 pounds per week. In addition, we will carefully monitor changes in weight during our trial. We will collect information at each assessment timepoint on hospitalizations for any psychiatric problem, including depression and eating disorders.

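### The FRAIL weight-loss item does not exclude intentional loss, so weight loss brought about by the programme can count as frailty and mask or reverse improvement

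*Combined protocol and SAP*

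**What the plan says.** Section 3 (Anthropometric and clinical measures) describes the frailty measure: "The items assess: 1) self-reported fatigue (PROMIS Fatigue Short form), 2) weight loss, 3) comorbidities", followed by difficulty with ambulation and ability to overcome resistance. The other four items each have a named source: PROMIS short forms for fatigue, ambulation and resistance, and a registry assessment for comorbidities. The weight-loss item has none, and no amount, period or intent is given.

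Scoring is a simple count: "The number of positive responses for these components is summed to create the FRAIL index (range 0–5"), with participants "characterized as 0-1: robust, 2: prefrail, and 3+: frail". The paragraph ends: "Changes in individual components and overall frailty scores will be assessed".

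The Protocol Synopsis lists "clinical (Fried physical phenotype using the FRAIL index") among the secondary outcomes for which the main effect of each of the four components is estimated at 3 months. Weight stands in the same objective. Section 4 (Statistical Analysis) applies two analyses to these measures: Wilcoxon signed-rank tests of change from zero within each experimental condition, and mixed models with component-by-time terms.

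On weight loss itself, Section 5 (Participant Safety, Unsafe Rate of Weight Loss) states: "Participants will not receive an intervention designed to produce weight loss". The same sentence goes on to say that "making dietary changes and increasing PA can produce a gradual, modest rate of weight loss". Under Protections Against Risk, participants "will be taught that the appropriate rate of weight loss is 1 to 2 pounds per week". Section 2 (Study Design) lists daily self-weighing among the self-regulation strategies and weight change among the things participants evaluate weekly. The Psychological Risks paragraph says the content teaches the benefits of daily self-weighing for managing weight.

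**The concern.** Weight loss is meaningful as a frailty sign when it is not sought. In this trial some participants may lose weight because they eat better and move more, and the item as described does not separate the two. The same loss could then be read as a change in weight under one secondary outcome and as a new deficit under another.

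The limitations text in Section 4 presents the trial as the first intervention for this population to target determinants of frailty, and its findings are meant to inform later optimization trials. A frailty result that is flat or adverse because of one ambiguous item could misdirect that work.

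**Working it through.** The plan gives no expected value, variability or power for FRAIL, so there is no figure to reproduce. The check has three steps.

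**Step 1. What the item leaves open.** Threshold, look-back and intent are unstated. So is the source. Weight is measured on a home scale at baseline and 3 months, but at baseline there is no earlier study weight from which to compute a loss. A scale-based item therefore could not be scored at baseline without other information, and a scale reading does not record intent. The measure is called both a Fried index and the FRAIL questionnaire, so its name does not settle which definition applies.

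**Step 2. Where the item enters the analysis.** The total is the sum of five 0/1 items, so

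mean FRAIL = (sum of the shares positive on the other four items) + (share positive on weight loss).

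- One participant: a score of 1 plus a newly positive weight-loss item is 2, which crosses from robust to prefrail.
- Within-condition change: a rise of *d* in the share positive on this item adds *d* to the mean change, whether the loss came from the core programme or from a component.
- Component main effect: the shift is (rise at one level) − (rise at the other level). If the core programme produces the same rise *d* at both levels, the shift in the mean contrast is *d* − *d* = 0. Bias needs the two levels to differ.

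A difference between levels is plausible but not shown. The dietary factors contrast tracking low-calorie with high-calorie foods, and daily food goals with none. Section 1.3 says earlier work with the same tracking approach showed promise for weight loss in young adults.

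**Step 3. Illustration.** All item rates here are assumptions, and items are taken as independent. P(score ≥ 2) is 1 − P(0) − P(1).

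| Scenario | Other four items, each | Weight-loss item | Mean | P(score ≥ 2) |
|---|---|---|---|---|
| Baseline | 15% | 10% | 4 × 0.15 + 0.10 = 0.70 | 14.6% |
| Others improve, weight item steady | 10% | 10% | 4 × 0.10 + 0.10 = 0.50 | 8.1% |
| Others improve, weight item rises | 10% | 30% | 4 × 0.10 + 0.30 = 0.70 | 14.0% |
| Others improve, weight item rises further | 10% | 50% | 4 × 0.10 + 0.50 = 0.90 | 19.8% |

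The improvement in the other items is worth 4 × 0.05 = 0.20 points. A rise of 0.20 in the weight-loss item cancels it, and a larger rise reverses the sign. On the 0–4 score without the item, the change is 0.60 to 0.40 in every scenario.

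**The case against.** The strongest reply is that the paragraph lists domains in shorthand. The index was used before in young survivors and a source is cited, so the instrument may already carry a cut-off and an intent qualifier. That stands against the reading that the plan scores any weight loss as a deficit. A reader might infer this, but the text is silent and does not say so. Nor can one say that the point was absent at baseline, since the item is also collected then with an unstated look-back. What remains is that the plan does not say how loss caused by the programme is scored.

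A reader might also infer that the programme expects weight loss, and multiply the taught rate by 12 weeks to get 12–24 lb. The documents do not support that. They say the intervention is not designed for weight loss and that a gradual, modest loss is possible. The rate appears as safety advice, not as a target or forecast.

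Third, components are judged mainly on MVPA and diet quality, and loss due to the core programme is common to all 16 conditions. Both points are right. They confine the main-effect concern to factors whose levels differ in weight loss, but leave the within-condition tests exposed.

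Fourth, individual items will be reported, and weight is an outcome in its own right. This would help a reader detect the problem, but it does not correct the total or the categories.

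Finally, this is a feasibility pilot, and Section 4 already warns that effect sizes may be inconclusive. Assume an SD of FRAIL change of 0.7–1.0 and 40 per level (half of 80). The standard error of a main effect is then SD × √(2/40), about 0.16–0.22. An assumed bias of 0.1–0.2 is about 0.4–1.3 standard errors. That limits the consequence without removing it.

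**Conclusion.** The point holds as a defect in how a secondary outcome is defined. Scored as described, the total and the robust/prefrail/frail classes can absorb an effect of the programme as a deficit. This can hide or reverse improvement in the within-condition change tests. It can do the same in a component's main effect if the two levels of that component differ in weight loss.

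The documents do not allow the size to be derived. The shift in the mean contrast equals the between-level difference in the rise in the share scored positive because of intended loss. A difference of 10–20 percentage points, which is an assumption, would give 0.1–0.2 points toward apparent harm. A reader might conclude that effective components will look harmful. The documents do not support that either: they give no evidence that any factor's levels differ in weight loss, and effectiveness is not defined by weight. The point does not touch the primary feasibility endpoints, but the outcome should be corrected before it is analysed.

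**What to change.** Define the weight-loss item so that it is positive only when the participant reports the loss as unintentional. State its threshold, look-back period and data source, and apply the same definition at baseline and 3 months. This needs one question in the existing online survey.

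Pre-specify, as a sensitivity analysis, the change in FRAIL without the weight-loss item (0–4). Use it in both the within-condition tests and the component models. It uses data already collected.

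The costs are small: one question, one extra analysis, and slightly less comparability with earlier use of the index. Reported intent may also be influenced by assignment, for example by receiving dietary goals. The 0–4 score avoids that weakness, so the two should be reported together.

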### ***Psychosocial mediators and consequences (collected at baseline and 3 months)***

Health-related Quality of Life: will be assessed using the AYA PROMIS PRO Core battery, which has recently been recommended by the National Cancer Institute’s Clinical Trials Network AYA PRO Task Force. These measures assess relevant HRQoL domains for AYA cancer survivors that are most likely to be impacted during and after cancer treatment. The AYA PRO Core battery includes the following PROMIS short forms: depression, anxiety, fatigue,

physical function, pain interference, emotional support, cognitive function, pain intensity. Each question has five responses ranging in value from 1 to 5, which are summed to find the total raw score. Total raw scores are translated to a T-score, standardized with a population mean of 50 and a standard deviation of 10. A higher PROMIS T-score represents more of the concept being measured.

**Depressive Symptoms:** Depressive symptoms have been associated with changes in weight, diet, and PA and will be assessed with the PROMIS v1.0-Depression Short Form 4a.

**Anxiety.** Anxiety will be assessed using the PROMIS v1.0-Emotional Distress Anxiety Short Short Form 4a.

**Fatigue.** Fatigue will be assessed using the PROMIS v1.0-Fatigue Short form 4a.

**Physical Function.** Physical function will be assessed using the PROMIS v2.0 Physical function Short Form 4a.

**Pain Interference.** Pain interference will be assessed using the PROMIS Short form v1.1 Pain Interference Short Form 4a.

**Emotional Support.** Emotional support will be assessed using the PROMIS v2.0 Emotional Support Short form 4a.

**Cognitive Function.** Cognitive function will be assessed using the PROMIS v2.0 Cognitive function short form 4a.

**Pain Intensity.** Pain intensity will be assessed with the 1-tiem PROMIS v1.0 pain intensity 1a, "In the past 7 days, how would you rate your pain on average?" Scored 0-10 from no pain to worst imaginable pain.

**Competence for Exercise and Nutrition.** The Perceived Competence Scale includes 4 items that measure perceived competence for nutrition and 4 items for physical activity. Ratings are on a 7-point Likert scale with higher scores indicating greater perceived competence for the behavior.

**Self-efficacy for Exercise and Nutrition:** Nutrition and exercise self-efficacy will be measured using the Nutrition and Physical Activity Self-Efficacy Scale, a 10-item scale that assesses an individual's confidence in their ability to eat healthy foods and exercise in the presence of barriers. Ratings are on a 4-point Likert scale with higher scores indicating greater self-efficacy for exercise and nutrition.

**Self-Regulation for Exercise and Nutrition.** The Treatment Self-Regulation Questionnaire (TSRQ) will be used to assess autonomous and controlled motivation for making changes in diet (15 items) and PA (15 items). Ratings are on a 7-point Likert scale indicating agreement with statements regarding motivation for behavior change such as, "try to exercise on a regular basis: because I enjoy exercising." This questionnaire contains four subscales: external regulation, introjected regulation, identified regulation, and intrinsic motivation which are determined by averaging the responses to each of the subscale's items.

**Autonomy Support and Relatedness:** The Virtual Care Climate Questionnaire (VCCQ) a 15-item measure of perceived support for autonomy provided by the study team in a virtual care setting. Ratings are on a 7-point Likert scale with higher scores indicating a higher level of perceived autonomy support.

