## **3. STUDY PROCEDURES**

### **Data Collection**

All study participants will complete objective weight measurements, two dietary recalls, and self-administered online surveys at baseline and 3 months (post-intervention). At 6 weeks, only psychosocial measures and medical events will be collected via online survey and telephone. Participants will receive \$25 for completing the 3-month assessments. Online surveys will include measures of theoretical mediators, other psychosocial constructs, and process measures. We will send emails and texts prompting participants to complete assessments, with follow-up emails and phone calls to non-respondents, as necessary. Measures and timing are described below.

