### Statistical Analysis

Primary Endpoint Analysis. *Accrual rate* will be defined as the number of YACS who agreed to participate divided by the number of weeks of recruitment. *Participation rate* will be defined as the percent of eligible participants who agreed to participate. *Retention rate* will be defined as the number of participants who completed 3-month measures divided by the number who consented to participate. Means and 95% confidence intervals will be computed for all rates. The proportion of patients who complete the 3-month assessment will be reported along with an exact 95% confidence interval. This percentage will also be reported for experimental condition individually. We will test the hypothesis that the recruitment rate is  $\leq 50\%$  vs.  $\geq 65\%$  using a one-sample test of proportions with a one-sided alpha level of 0.05. We will test the hypothesis that the retention rate is  $\leq 70\%$  vs.  $\geq 90\%$  using a one-sample test of proportions with a one-sided alpha level of 0.05. We will use a one-sample Poisson test to compare the average number of participants accrued per month with a null hypothesis of 12 participants per month and a one-sided alternative of 14 participants per month at an alpha level of 0.05.

Secondary Endpoint Analysis. Ratings of program acceptability and satisfaction will be summarized using descriptive statistics (mean, standard deviations, frequencies) of the post-treatment evaluation (Objective 2.1.3). Descriptive statistics (percentages, medians, interquartile ranges) will be used to estimate adherence to daily self-monitoring (Objective 2.1.4), and study measures relating to demographics, anthropometric, clinical, behavioral, and psychosocial measurements (Objectives 2.1.5-2.1.7.). These study measures will be reported at baseline and 3 months. We will also estimate changes in weight, anthropometric, clinical, behavioral, and psychosocial measures from baseline to 3 months, and within each experimental condition, the change scores

will be tested to see if they are significantly different from 0 using Wilcoxon Signed Rank tests.

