- C) Advertisements. We will place sponsored posts on social media, ads on relevant internet sites, and use email listservs. We will produce flyers, posters, brochures, and presentations to advertise the study at community events and cancer conferences dedicated to young adults (e.g., CancerCon, AYA Global Congress). We will work with the UNC AYA Oncology clinical staff with whom we have established relationships (i.e., Co-Investigator [name], Medical Director, UNC AYA Oncology; [name]) to advertise the study and recruit potentially interested individuals.

All recruitment efforts will direct participants to a study website with a more detailed description of the research study and FAQs about participating in research. Interested individuals will click through to a REDCap web screening survey to determine initial eligibility. Those who are preliminarily eligible will be contacted by trained study staff and will undergo additional phone screening. Following an approach we have used in the past, eligible and interested individuals will receive an email directing them to a unique REDCap link to an online informed consent. After providing consent, participants will be instructed on procedures for 1) completing one weekday and one weekend self-reported 24-hour dietary recall, 2) completing baseline online questionnaires, and 3) completing their baseline weight measurement. The Fitbit activity tracker will be mailed to the participant. After completion of baseline assessments, the participant will be randomized to one level of each of the 4 factors, or one of the 16 conditions (Table 1). The participant will be scheduled for a one-on-one telephone/videochat session during which they will be informed of condition assignments, assisted with downloading of the study smartphone app, and questions about getting started will be answered.

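### The VCCQ rates support from the study team but is scheduled at baseline, before any programme care, so its within-condition change from baseline cannot be interpreted

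*Combined protocol and SAP*

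**What the plan says.** Section 3, Measures, under Autonomy Support and Relatedness, describes the VCCQ as "a 15-item measure of perceived support for autonomy provided by the study team in a virtual care setting". The block heading above it reads "Psychosocial mediators and consequences (collected at baseline and 3 months". Unlike the headings for the anthropometric, supporting and other measures, it carries no clause allowing exceptions. The VCCQ entry itself gives no different timing, no baseline rewording and no other care provider to rate.

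The Data Collection paragraph likewise places "self-administered online surveys at baseline and 3 months (post-intervention", but adds: "At 6 weeks, only psychosocial measures and medical events will be collected via online survey and telephone". The block heading omits that 6-week wave.

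The Recruitment section gives the order of events. After consent, participants are instructed on several tasks, including "completing baseline online questionnaires". Then: "After completion of baseline assessments, the participant will be randomized to one level of each of the 4 factors, or one of the 16 conditions". The one-to-one session that reveals the assignment and helps with the app is described after that.

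The Statistical Analysis section states: "We will also estimate changes in weight, anthropometric, clinical, behavioral, and psychosocial measures from baseline to 3 months", with change scores within each experimental condition tested against 0 by Wilcoxon signed-rank tests. It also plans mixed models with component, time and component-by-time terms for MVPA, HEI and other secondary measures. No analysis of the VCCQ at 3 months alone is described.

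**The concern.** A depression or self-efficacy score describes the participant and has a natural value before treatment. The VCCQ describes how someone else behaves towards the participant, and here that someone is the study team. At baseline the team has delivered no programme care. The answers can reflect only recruitment contact, or a guess. At 3 months the same items refer to the programme, so the difference does not measure movement on one scale.

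The VCCQ is the plan's listed measure of autonomy support and relatedness, and perceived relatedness is what the text messages are meant to influence. The pilot is intended to inform later optimisation trials, so a mistimed mediator could be carried forward into them.

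**Working it through.** The plan states no mean, SD, correlation, effect size or power for the VCCQ, so there is no figure to reproduce. The check has three parts.

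**1. What has happened by baseline.** The Informed Consent and Recruitment sections describe web and telephone screening, an explanation of the study, online consent, and instructions for the baseline tasks. The introductory session appears under Elements Common to All Experimental Conditions. It covers the app, the tracker, the food log and information on the assigned conditions, so it follows randomisation. No programme care precedes the baseline rating.

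**2. Change within a condition.** The score is (3-month rating of the programme) minus (baseline rating of recruitment contact). A mean of 0 would not show that support was unchanged, and a non-zero mean would not show that it improved or worsened. This holds whatever the correlation between the two ratings. The test also has little to offer: with 5 participants per cell, as planned for 80 evaluable participants in 16 cells, the smallest exact two-sided signed-rank p-value is 2/2^5 = 0.0625. That second limit applies to every measure, not only to the VCCQ.

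**3. Contrast between component levels.** Let r be the baseline to 3-month correlation and k = baseline SD / 3-month SD. Neither is in the documents, so both are varied. With two waves and complete data, the component-by-time estimate equals the difference in change scores. Relative to comparing 3-month scores:

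- variance ratio = 1 + k² − 2rk, and the standard error (SE) ratio is its square root
- break-even at r = k/2
- with k = 1, variance ratio = 2(1 − r) and break-even at r = 0.5

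| r | SE ratio, k = 1 | Power, change score | Power, 3-month score |
|---|---|---|---|
| 0 | √2.0 = 1.41 | 35% | 61% |
| 0.3 | √1.4 = 1.18 | 47% | 61% |
| 0.5 | √1.0 = 1.00 | 61% | 61% |
| 0.7 | √0.6 = 0.77 | 82% | 61% |

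The power columns assume 40 participants per level (80/2), two-sided alpha 0.05, equal SDs and a standardised difference of 0.5. That difference is an illustration, not a planning value from the documents.

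If baseline answers cluster, k falls below 1. With k = 0.5, the SE ratio is √1.25 = 1.12 at r = 0 and √(1.25 − 0.3) = √0.95 = 0.97 at r = 0.3.

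Simulating the 16-cell design with 5 per cell, a true component difference of 0.5 and k = 1 gave mean change-score estimates between 0.49 and 0.51, so there was no bias. The simulated variance ratios were 1.73, 1.38 and 1.03 at r = 0.1, 0.3 and 0.5, against 1.8, 1.4 and 1.0 from the formula. A fitted random-intercept model returned the same component-by-time estimate as the difference in change scores.

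**Baseline as a covariate.** The variance ratio against 3-month scores alone is 1 − r²: 1.00 at r = 0, 0.91 at 0.3, 0.75 at 0.5 and 0.51 at 0.7. Used this way, a baseline rating costs essentially no precision and helps if r is substantial.

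**The case against.** A reader might infer that every change analysis of the VCCQ is meaningless, or that the baseline rating is bound to add noise. The documents support neither. Baseline precedes randomisation, so the component-by-time contrast remains unbiased for the 3-month difference between levels. A precision loss needs r below k/2, which the documents cannot settle; above that value the change score is the more precise of the two. A low r is a reasonable expectation when the two ratings concern different things, but it remains an assumption.

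It could also be said that within-condition change cannot be attributed to the intervention for any measure, because everyone receives the core programme and there is no untreated arm. That is true, but it is a separate matter. The problem specific to the VCCQ is that the two ratings have different objects.

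The block heading covers many instruments and already disagrees with Data Collection about 6 weeks, so it may simply be loose. That is possible, but a team following the text would give the VCCQ at baseline. Whether its items can be answered from recruitment contact depends on their wording, which the documents do not reproduce; even if they can, the contact rated is not the programme.

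The limit on stakes stands in full. The synopsis names only health-related quality of life as the psychosocial outcome, and no mediation analysis is described. The VCCQ enters the change analyses only through general wording about psychosocial and other secondary measures. Tailored feedback goes to all participants, so no component contrast tests it.

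**Conclusion.** The point holds in a limited form. If the plan is followed as written, the within-condition VCCQ change and its test against 0 are not interpretable. That conclusion rests on the described order of events and on the plan's own account of what the VCCQ rates, not on any assumed number.

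For the component contrasts the issue is precision, not validity, and its direction is unknown. Over the values examined, the SE ratio runs from 1.41 (r = 0, equal SDs) to 0.77 (r = 0.7, equal SDs), with 1.12 to 0.97 for k = 0.5 and r from 0 to 0.3. These figures assume complete data and two waves.

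The effect is confined to one supporting mediator measure. Participation, accrual and retention are unaffected, as are the MVPA and HEI analyses. It is a low-cost correction worth making, not a threat to the trial's main conclusions.

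**What to change.** State in the VCCQ entry that it is collected only after the intervention starts: at 3 months, and at 6 weeks if the Data Collection statement on psychosocial measures applies to it. Reconcile that statement with the block heading.

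In the Statistical Analysis section, compare 3-month VCCQ scores between the two levels of each component, and exclude the VCCQ from the change-from-baseline summaries, the Wilcoxon tests and the component-by-time models. The plan already treats program acceptability and satisfaction this way, as a post-treatment evaluation only.

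If the team prefers to keep a baseline rating, use it only as a covariate for the 3-month score, say that it reflects recruitment contact, and drop the test of change against 0.

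The cost is an edit to the survey schedule and a few lines of analysis text; the baseline survey becomes 15 items shorter. The downside is having no baseline VCCQ value to adjust for, which would matter only if r proved substantial: at r = 0.7 adjustment would have cut the variance to 0.51 of the unadjusted value, but at r = 0.3 only to 0.91.
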